9.6 Secondary Efficacy Analyses

To assess the treatment effect on the change of body weight in subjects with baseline BMI ≥ 25 kg/m² at week 60, an analysis of covariance model (ANCOVA) will be implemented using all available data at week 60 (values obtained after the start of rescue medication will not be excluded in the analysis). The model will include treatment, randomization stratification factors, and the baseline weight value as fixed effects/covariates. Least squares mean treatment differences between the bexagliflozin group and the comparator group will be estimated from the model. The corresponding 95% CI and p-value will be provided.

The change in systolic blood pressure (SBP) in subjects with baseline SBP ≥ 140 mmHg in the bexagliflozin group compared with glimepiride group at week 60 will be analyzed using the same method.

The difference in proportion of subjects with ≥ 1 severe or documented symptomatic hypoglycemia events in the bexagliflozin group compared with glimepiride group over 96 weeks will be analyzed using logistic regression model which includes terms of treatment, randomization stratification. Odd ratio estimates, 95% two-sided confidence intervals and p-values for the treatment difference will be provided.

All analyses will be conducted in ITT analysis set. A hierarchical testing procedure will be applied to above three endpoints in the sequence provided above.

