3.2. SECONDARY OBJECTIVES

- To evaluate the treatment effect of bexagliflozin vs. glimepiride on the change in body weight in subjects with baseline body mass index (BMI) ≥ 25 kg/m² at week 60
- To evaluate the treatment effect of bexagliflozin vs. glimepiride on the change in systolic blood pressure (SBP) in subjects with baseline SBP ≥ 140 mmHg at week 60
- To evaluate the treatment effect of bexagliflozin vs. glimepiride on the difference in proportion of subjects with ≥ 1 severe or documented symptomatic hypoglycemia events over 96 weeks
- To evaluate if bexagliflozin is superior to glimepiride on HbA_{1c} reduction at week 60

3.3. EXPLORATORY EFFICACY OBJECTIVES:

- To assess the treatment effect of bexagliflozin vs. glimepiride on the change in the proportion of subjects achieving HbA_{1c} $< 7.0\%$ over time
- To assess the treatment effect of bexagliflozin vs. glimepiride on the change in HbA_{1c} over time
- To assess the treatment effect of bexagliflozin vs. glimepiride on the change in fasting plasma glucose (FPG) over time
- To assess the treatment effect of bexagliflozin vs. glimepiride on the change in SBP over time
- To assess the treatment effect of bexagliflozin vs. glimepiride on the change in body weight over time
- To assess the treatment effect of bexagliflozin vs. glimepiride on the difference in proportion of subjects with ≥ 1 severe or documented symptomatic hypoglycemia events over time

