4.2. SECONDARY EFFICACY ENDPOINTS

- Change from baseline to week 60 in body weight in subjects with baseline body mass index (BMI) ≥ 25 kg/m²
- Change from baseline to week 60 in SBP in subjects with baseline SBP ≥ 140 mmHg
- Difference in proportion of subjects with ≥ 1 severe or documented symptomatic hypoglycemia events over 96 weeks
- Change from baseline to week 60 in HbA_{1c}

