8.2. SECONDARY EFFICACY ENDPOINT(S) AND ANALYSES

The secondary endpoints will only be tested when the non-inferiority of the primary efficacy assessment is established at one-sided significance level of 0.025. To control the overall type I error of 0.05, the secondary efficacy objectives will be tested at one-sided 0.025 significance level following the sequence below:

- Superiority test of the change in body weight in subjects with baseline body mass index (BMI) ≥ 25 kg/m² at week 60.
- Superiority test of the change in SBP in subjects with baseline SBP ≥ 140 mmHg from baseline at week 60.
- Superiority test of the difference in proportion of subjects with ≥ 1 severe or documented symptomatic hypoglycemia events over 96 weeks

Analysis for secondary endpoints will be based on ITT analysis set and repeated for PP analysis set. For body weight and SBP, all post-baseline values up to week 60 will be used for model analysis. All values will be summarized.

8.2.1. Change in body weight in subjects with baseline body mass index (BMI) ≥ 25 kg/m² at week 60

This will be tested if the non-inferiority of HbA_{1c} and the previous secondary efficacy endpoints are significant. Data after rescue medication will not be excluded. The comparison of change in body weight between randomized treatments at week 60 will be carried out using the similar MMRM model as section 8.1.1 using all available data. The model will include terms for region, treatment, baseline HbA_{1c} as continuous variable, treatment background (metformin-only or metformin-and-OHA), and baseline eGFR (≥ 90 or < 90 mL/min/1.73 m²) as fixed effects and the corresponding baseline weight value as covariate. Treatment comparison p-values and difference at week 60 will be estimated from the model, with the two-sided 95 % CIs of the treatment difference also presented. If the superiority of HbA_{1c} is not established, the nominal p-value will not be used for inferential purposes. Summary table will be presented and figures will be displayed for ITT population.

8.2.2. Change in SBP in subjects with baseline SBP ≥ 140 mmHg from baseline at week 60

This will be tested if the change from baseline body weight is significantly different between bexagliflozin and glimepiride groups based on ITT analysis set for subjects with a BMI ≥ 25 kg/m². Change from baseline in SBP at week 60 will be analyzed in a similar manner as change in body weight, Section 8.2.1, based on ITT analysis set for all

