subjects. Baseline SBP will be used in place of baseline weight. Summary table will be presented and figures will be displayed for ITT population.

8.2.3. Difference in proportion of subjects with ≥ 1 severe or documented symptomatic hypoglycemia event over 96 weeks

This will be formally tested if the previous secondary efficacy endpoints are significant. Events after the start of rescue medication will be counted. Descriptive statistics of frequency and percentage will be provided. Logistic regression model will be used, with region, treatment, baseline HbA_{1c}, treatment background (metformin-only or metformin-and-OHA), and baseline eGFR (≥ 90 or < 90 mL/min/1.73 m²) as fixed effects. Odd ratio estimates, 95% two-sided confidence intervals and p-values for the treatment difference will be provided. Summary table will be presented and figures will be displayed for ITT population.

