Table 14.2.1.11	Analysis of Change from Baseline in HbA1c (%) at Week 60 by Baseline eGFR (ITT Analysis Set)
Table 14.2.1.12	Analysis of Change from Baseline in HbA1c (%) at Week 60 by Region (ITT Analysis Set)
Table 14.2.2.1	Analysis of Change from Baseline in Body Weight (kg) at Week 60 for Subjects with BMI \geq 25 kg/m ² (ITT Analysis Set)
Table 14.2.2.2	Analysis of Change from Baseline in Body Weight (kg) at Week 60 for Subjects with BMI \geq 25 kg/m ² (PP Analysis Set)
Table 14.2.2.3	Sensitivity Analysis: Multiple Imputation for Change from Baseline in Body Weight (kg) at Week 60 for Subjects with BMI \geq 25 kg/m ² Excluding Observations Obtained after Rescue Medication
Table 14.2.2.4	Analysis of Change from Baseline in Body Weight (kg) for Subjects with BMI \geq 25 kg/m ² over Time (ITT Analysis Set)
Table 14.2.3.1	Analysis of Change from Baseline in SBP (mmHg) at Week 60 for Subjects with Baseline SBP \geq 140 mmHg (ITT Analysis Set)
Table 14.2.3.2	Analysis of Change from Baseline in SBP (mmHg) at Week 60 for Subjects with Baseline SBP \geq 140 mmHg (PP Analysis Set)
Table 14.2.3.3	Sensitivity Analysis: Multiple Imputation for Change from Baseline in SBP (mmHg) for Subjects with Baseline SBP \geq 140 Excluding Observations Obtained After Rescue Medication (ITT Analysis Set)
Table 14.2.3.4	Analysis for Change from Baseline in SBP (mmHg) for Subjects with Baseline SBP \geq 130 over Time (ITT Analysis Set)
Table 14.2.3.5	Analysis for Change from Baseline in SBP (mmHg) for All Subjects over Time (ITT Analysis Set)
Table 14.2.4.1	Summary of Proportion of Subjects with \geq 1 Severe or Documented Symptomatic Hypoglycemia Event over 96 Weeks (ITT Analysis Set)
Table 14.2.4.2	Summary of Proportion of Subjects with \geq 1 Severe or Documented Symptomatic Hypoglycemia Event over 96 Weeks (PP Analysis Set)
Table 14.2.4.3	Sensitivity Analysis: Incidence Rate of Severe or Documented Symptomatic Hypoglycemia Event over 96 Weeks (ITT Analysis Set)
Table 14.2.4.4	Summary of Proportion of Subjects with \geq 1 Severe or Documented Symptomatic Hypoglycemia Event over Time (ITT Analysis Set)
Table 14.2.5	Analysis of Change from Baseline in FPG (mmol/L) Over Time (ITT Analysis Set)

Number	Title
Table 14.2.6	Summary of Proportion of Subjects with HbA1c < 7% Over Time (ITT Analysis Set)
Table 14.3.1.1	Overall Summary of Treatment-Emergent Adverse Events (Safety Analysis Set)

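### SAP 8.2.2 bases the confirmatory week 60 SBP test on all ITT subjects, while its own heading, the testing sequence, the planned tables and the protocol restrict it to baseline SBP ≥ 140 mmHg

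*SAP*

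**What the plan says.** SAP 8.2 lists the secondary tests in order, after non-inferiority on HbA1c: body weight, then SBP, then hypoglycemia. The SBP step reads "Superiority test of the change in SBP in subjects with baseline SBP ≥ 140 mmHg from baseline at week 60". The objective in SAP 3.2 concerns the "change in systolic blood pressure (SBP) in subjects with baseline SBP ≥ 140 mmHg at week 60", and the endpoint in SAP 4.2 is "Change from baseline to week 60 in SBP in subjects with baseline SBP ≥ 140 mmHg". Protocol 9.6 has the same population: "The change in systolic blood pressure (SBP) in subjects with baseline SBP ≥ 140 mmHg in the bexagliflozin group".

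SAP 8.2.2 carries the ≥ 140 mmHg limit in its heading. Its first sentence makes the SBP test conditional on the weight result, which it describes as "based on ITT analysis set for subjects with a BMI ≥ 25" kg/m². The next sentence says how SBP is handled: the week 60 change "will be analyzed in a similar manner as change in body weight, Section 8.2.1, based on ITT analysis set for all", and the text runs on, "subjects. Baseline SBP will be used in place of baseline weight". The population named there is every ITT subject.

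Under SAP 8.2.3, hypoglycemia is formally tested only if the preceding secondary endpoints were significant.

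**The concern.** The sentence that tells the programmer how to run the SBP test names a different population from the sequence that gives the test its confirmatory status. SBP results will exist in both populations. SAP 8.3.1 plans exploratory repeated-measures analyses of SBP over time for the ≥ 140 mmHg subset and for all subjects, with estimates at each visit and p-values. If the two week 60 p-values fell on opposite sides of the threshold, the SAP text could be cited for either one, and the answer would decide whether hypoglycemia may be formally tested. A correction made after unblinding could look like a choice made with the results in hand.

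**Working it through.** No arithmetic applies. The plan gives one sample-size calculation, for HbA1c, and none for SBP. The check is to set the relevant places side by side.

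| Place | Role | SBP population |
|---|---|---|
| SAP 3.2 | Secondary objective | ≥ 140 mmHg |
| SAP 4.2 | Secondary endpoint | ≥ 140 mmHg |
| SAP 8.2 | Confirmatory sequence | ≥ 140 mmHg |
| SAP 8.2.2, heading | Title of the analysis | ≥ 140 mmHg |
| **SAP 8.2.2, analysis sentence** | **How the test is run** | **All ITT subjects** |
| SAP 17, Tables 14.2.3.1 and 14.2.3.2 | Week 60 result, ITT and PP | ≥ 140 mmHg |
| SAP 17, Table 14.2.3.3 | Multiple-imputation sensitivity analysis | ≥ 140 mmHg |
| SAP 18, Figure 14.2.3 | Course over time | ≥ 140 mmHg |
| SAP 8.3.1; Table 14.2.3.5 | Exploratory, over time | All subjects |
| Protocol 2.2, 9.1, 9.6 | Objective, sequence, analysis | ≥ 140 mmHg |
| Protocol 9.7 | Other efficacy analyses | All subjects |
| SAP 13 | Changes from the protocol | No change of SBP population listed |

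The title of Table 14.2.3.1 begins "Analysis of Change from Baseline in SBP (mmHg) at Week 60 for Subjects with Baseline SBP" and continues with the 140 mmHg limit.

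1. **The conflict.** Within the confirmatory material, only the analysis sentence of 8.2.2 says all subjects. How many places disagree with it depends on the counting rule (contents entry, over-time figure, exploratory section), so nothing here rests on a count.

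2. **What the phrase may have meant.** The preceding sentence uses the same construction to confine the weight test to BMI ≥ 25 kg/m², and the SBP method is then borrowed from 8.2.1. The phrase can therefore be read as removing only the BMI limit and leaving the ≥ 140 mmHg limit in the heading to apply. It can equally be read as naming a population, because that is what the same construction does one sentence earlier.

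3. **The literal reading inside the SAP.** The main test would be in all subjects, while the sensitivity analysis meant to support it (Table 14.2.3.3) would be in the ≥ 140 mmHg subset. The two would address different questions. No table is titled for a confirmatory week 60 test in all subjects.

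4. **The gate.** Hypoglycemia requires primary non-inferiority, then a significant weight result, then a significant SBP result. The ambiguity affects only the SBP condition, but that condition must be met.

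**The case against.** The strongest reply is that the documents already settle the population. Heading, sequence, objective, endpoint, tables and protocol agree on ≥ 140 mmHg, SAP 13 declares no change, and all-subject SBP has its own exploratory place. A careful programmer would follow the table titles. The table shells and the SAP appendix were not available for this review and may state the subset outright. The model, data window and significance level come from 8.2 and 8.2.1, so the disputed clause is not the whole specification.

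Most of this stands. It makes the intended population clear and reduces the point to a wording correction. It does not remove the need for one: the population of a gating test should be stated correctly where the analysis is described, without the reader having to weigh one place against others.

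A reader might infer that the SAP moved the confirmatory SBP test to the whole ITT set. The documents do not support that. Such a change would belong in SAP 13, which is silent on it, and the reporting tables still carry the 140 mmHg limit.

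**Conclusion.** The contradiction is real and should be corrected before unblinding. It is small in extent: one clause in one sentence, most likely a slip. It matters because of where it sits, in the second of three ordered secondary tests, with hypoglycemia behind it.

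No numerical size is claimed. A reader might infer a specific gain or loss in the chance of reaching the hypoglycemia test, since all subjects outnumber the subset. The documents give no SBP standard deviation, no expected treatment difference and no share of subjects at or above 140 mmHg, and the effect may vary with baseline SBP, so no such figure can be derived. Nor does correcting the wording change the power of the test in the intended subset.

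A reader might also infer that error control is already broken. A fixed sequence protects the overall level with either population, provided that one is fixed in advance. The exposure is that the text leaves room to argue for either.

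The conclusion assumes only that the SAP text is as published and that the unseen shells do not override it.

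**What to change.** In the analysis sentence of SAP 8.2.2, replace the reference to all subjects with *for subjects with baseline SBP ≥ 140 mmHg*. Adding *regardless of BMI* is optional; it would stop the cross-reference to 8.2.1 from being read as importing the BMI limit.

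Add one sentence saying that, for the SBP step of the sequence, the ≥ 140 mmHg result counts and the all-subject result does not; that primary non-inferiority and the body-weight step are still required first; and that all-subject SBP stays exploratory under 8.3.1. The sentence should not say that SBP alone opens the hypoglycemia test, because the earlier steps do so as well.

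Separately, and with no bearing on the confirmatory test, the title of exploratory Table 14.2.3.4 gives a cut-off of 130 mmHg where 8.3.1 gives 140. Align the two.

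The cost is a few words in the SAP and one table title, made before unblinding. It needs no protocol amendment, no new data and no change to the order of testing.

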7.2.2 Run-in Period

7.2.2.1 Visit V4 (2 weeks prior to randomization)

- Counsel subject on appropriate diet and exercise (for subjects who receive metformin only and do not need a washout)
- Dispense glucometer and instruct subject in SMBG determination and recording (for subjects who receive metformin-only)
- Review SMBG and glycemic control record (for subjects who receive metformin + 1 OHA)
- Dispense run-in kits for run-in period
- Measure vital signs, including blood pressures and heart rate
- Assess adverse events and potential DKA
- Record pre-treatment medications

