3.8. DETERMINATION OF SAMPLE SIZE

An approximate total of 420 subjects will be randomized and equally allocated to receive:

- bexagliflozin tablets, 20 mg and glimepiride, placebo capsules (referred to as bexagliflozin group in this document)
- bexagliflozin tablets, placebo and glimepiride capsules, 2 mg, 4 mg, or 6 mg (referred to as glimepiride group in this document).

The sample size calculation for this study is based on a two group t-test with a one-sided significance at the 0.025 level and the following assumptions:

- The non-inferiority limit (margin) for mean change from baseline to week 60 in HbA_{1c} comparing bexagliflozin group to glimepiride group will be 0.35%
- The standard deviation for the change from baseline to week 60 in HbA_{1c} for bexagliflozin group and glimepiride group will be 1.0%

Under the above assumptions, an estimated sample size of 172 subjects is needed in each treatment arm to determine non-inferiority of bexagliflozin to glimepiride with respect to change in HbA_{1c} at week 60 from baseline. This estimation is based on a one-sided t-test with 90% power at a 0.025 level of significance. A sample size of 210 per arm has been selected to account for approximate 18% drop-out rate and to allow adequate safety evaluation. The total sample size for this study will be 420 subjects.

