6.2. KEY DEFINITIONS

6.2.1. Baseline Values

For subject who is dosed, baseline is defined as the last non-missing value on or prior to the first dose of double-blind study medication. For subject who is not dosed, baseline is defined as the last non-missing value on or prior to the randomization date.

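### The SBP key secondary adjusts for the V5 value only, leaving the V1 and V4 pre-treatment SBP unused and giving up some precision in the test that gates hypoglycemia

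*SAP*

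**What the plan says.** SAP 8.2.1 sets the template for the weight analysis: a repeated-measures model with treatment, region, baseline HbA1c, treatment background, baseline eGFR category and one baseline value of the endpoint. SAP 8.2.2 carries this over to SBP: "Baseline SBP will be used in place of baseline weight".

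SAP 6.2.1 fixes which value that is. For a dosed subject, "baseline is defined as the last non-missing value on or prior to the first dose of double-blind study medication". The schedules (Protocol Appendix 1, SAP Table 1) place vital signs at V1, V4 and V5 but not at V6, so baseline SBP is normally the V5 value, taken 3 to 5 days before randomization. Protocol 7.2.2.1 requires the same measurement at V4 ("Measure vital signs, including blood pressures and heart rate"), and Protocol 7.1.1 requires it at V1. Neither value appears in any efficacy model.

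Three further provisions matter:

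- Protocol 5.2.4 bars adjustment of diuretics and antihypertensives in screening, washout and run-in. Protocol 4.3 excludes SBP above 160 mmHg at V1.
- In SAP 8.2, "the secondary efficacy objectives will be tested at one-sided 0.025 significance level following the sequence below", with SBP second. For hypoglycemia, which is third, SAP 8.2.3 says: "This will be formally tested if the previous secondary efficacy endpoints are significant".
- The heading of SAP 8.2.2 and the list in 8.2 restrict the SBP test to baseline SBP ≥ 140 mmHg, but the body text of 8.2.2 says the analysis covers all subjects in the ITT set.

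**The concern.** SBP at one visit is a noisy measure of a subject's usual SBP. Two further pre-randomization measurements, on unchanged blood-pressure drugs, are collected for every subject. Averaging over visits should predict week-60 SBP better than V5 alone, and whatever the covariates do not explain stays in the residual variance of the treatment comparison.

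The position of the test raises the stakes. The SBP test uses only part of the randomized population, no power is stated for it, and if it fails there is no formal hypoglycemia claim. Precision given up here is therefore given up for two key secondaries.

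**Working it through.** **1. The plan's own figure.** The only sample-size calculation is for HbA1c, "based on a two group t-test with a one-sided significance at the 0.025 level", with 90% power, margin 0.35 and SD 1.0. n = 2 × (1.960 + 1.282)² × 1.0² / 0.35² = 171.6, so 172 per arm; 172 / (1 − 0.18) = 209.8, so 210. It reproduces, and it says nothing about SBP.

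**2. Formula.** Let r_b be the correlation between any two pre-treatment SBP values, and r_f that between a pre-treatment value and week 60. As a fraction of total variance, the week-60 residual variance is:

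- V5 only: 1 − r_f²
- V1, V4 and V5: 1 − 3r_f² / (1 + 2r_b)

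This treats the comparison as an analysis of covariance at week 60, which approximates the repeated-measures model.

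**3. Equal correlations (r_b = r_f = ρ).** At ρ = 0.5 the two values are 0.750 and 0.625, a cut of 1 − 0.625/0.750 = 16.7%.

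| ρ | 0.3 | 0.4 | 0.5 | 0.6 | 0.7 |
|---|---|---|---|---|---|
| Cut in residual variance | 8.7% | 12.7% | 16.7% | 20.5% | 24.0% |

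**4. Pre-treatment values more alike than they are like week 60.**

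| r_b / r_f | 0.7/0.6 | 0.6/0.5 | 0.7/0.5 | 0.6/0.4 | 0.8/0.5 | 0.7/0.3 |
|---|---|---|---|---|---|---|
| Cut | 14.1% | 12.1% | 8.3% | 6.9% | 5.1% | 2.5% |

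**5. What the cut-offs do.** In simulation with V1 ≤ 160 and V5 ≥ 140 (assumed mean SBP 128–132, SD 13–15), the cut falls from 16.7% to about 14–15% at ρ = 0.5, and from 20.5% to about 18–19% at ρ = 0.6. Selection does narrow V5: with mean 130, SD 14 and ρ = 0.5, V5 explains 6.1% of week-60 variance inside the subset, against ρ² = 25% without selection. But the residual SD given V5 is 12.0 inside the subset, against 14 × √0.75 = 12.1 without selection. The unexplained variance is essentially unchanged.

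**6. Variance-component range.** Each SBP value is a stable level plus slow drift (shared by the pre-treatment visits, independent at week 60) plus visit noise. Assumed: mean 130–134, between-subject SD 10–12, drift SD 0–6, visit SD 8–11 mmHg. The two ends:

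- SDs 12, 0, 8: ρ = 144/208 = 0.69. Closed form 23.8%; about 21% inside the subset.
- SDs 10, 6, 11: r_b = 136/257 = 0.53, r_f = 100/257 = 0.39. Closed form 8.2%; about 7% inside the subset.

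The range inside the subset is therefore about 7–21%. That equals 1/0.93 = 1.08 to 1/0.79 = 1.27 times the subjects, or about 8–27% more.

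**7. Power.** Assume 25% of subjects are in the subset: 210 × 0.25 × 0.82 = 43 evaluable per arm. Take a 5 mmHg effect and one-sided 0.025, with power = Φ(5 / (SD × √(2/43)) − 1.96).

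- SD 12, V5 only: 5/2.588 − 1.96 = −0.03, power 49%.
- Variance cut 9%: SD 11.45, power 53%.
- Variance cut 18%: SD 10.87, power 57%.

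Over all the step 6 scenarios, power moves from 34–64% to 36–73%, a gain of about 2–10 points.

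**The case against.** The strongest reply is that nothing here is an error. Adjusting for one prespecified baseline value is ordinary practice, and Protocol 9.6 prescribes it. Selection on V5 acts alike in both randomized arms, so the test is valid. That stands in full: the point is an efficiency gain.

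Second, the gain is modest and rests on assumptions. A test with 40–50% power stays near that level in many scenarios. This also stands; the case for the change is that it needs no new data.

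Third, V1 is not perfectly comparable. Metformin-and-OHA subjects have V1 before the second agent is stopped and up to 9 weeks before run-in, while metformin-only subjects have it at most 3 weeks before. Blood-pressure drugs may also change during treatment, which can weaken the link of any pre-treatment value to week 60. This pushes towards the lower end of the range but does not remove the gain. V4 follows washout, and adding V4 alone gives 11.1% of the 16.7% at ρ = 0.5.

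A reader might also infer that the 140 mmHg cut-off causes the loss by making V5 a weak predictor. Step 5 shows otherwise: the cut-offs slightly shrink the available gain. The loss comes from visit-to-visit noise. Nor is 140 mmHg a trial-entry limit; that limit is SBP above 160 mmHg at V1.

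**Conclusion.** The point holds as a free improvement in precision. V1 and V4 SBP are collected before randomization under fixed blood-pressure drugs and are left out of the model for a key secondary that gates another. Under the stated variance assumptions, using them cuts residual variance by about 7–21% in the subset and adds about 2–10 points of power at 43 per arm and 5 mmHg. The cut could be about 5% or less if pre-treatment values correlate much more with each other than with week 60.

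No single percentage can be stated as fact, because the documents supply none of the SBP inputs. That the subset is small is likewise an inference (17–33% of subjects across the assumed scenarios), and SAP 8.2.2 contradicts itself on whether the subset is the population analysed. A reader might infer that hypoglycemia should therefore be tested before SBP. That does not follow: the order is a choice of claim priority, set consistently in Protocol 9.1 and 9.6 and SAP 8.2. Moving hypoglycemia up would make the SBP claim depend on it instead.

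**What to change.** Before unblinding, make one edit to SAP 8.2.2:

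1. Add the mean of the V1 and V4 sitting SBP as a further covariate. Keep V5 as the baseline that defines the ≥ 140 mmHg subset and the change score, and as the existing covariate.
2. State that the endpoint is sitting SBP. Protocol 6.7 records three positions, and SAP 9.5 ties the sitting value only to eligibility.
3. Say what is done if V1 or V4 is missing, for example using the one that is available.
4. Reconcile the words extending the analysis to all subjects with the section heading and the test listed in SAP 8.2.

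Record the added covariate in SAP section 13 as a change from the protocol. The cost is a few sentences and one derived variable. There is no new visit, measurement or burden on subjects. As a prespecified pre-randomization covariate, it leaves the treatment contrast being estimated and the type I error unchanged.
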